1.2 SCHEDULE OF ACTIVITIES (SOA)

Procedures	Online Prescreen	Virtual Visit	Study visit 1	Study Visit 2	7 day Remote Assessment	Discharge visit
Online prescreen survey	X					
Informed consent		X				
DSM-5 SCID AUD and SUD		X				
Demographics Form		X				
Alcohol Use Identification Test (AUDIT)		X				
Inventory of Drinking Situations (IDS)		X				
Obsessive Compulsive Drinking Scale (OCDS)		X				
Reward-based Eating Drive Scale (RBEDS)		X				
Body Perception Questionnaire (BPQ)		X				
Drinking Motives Questionnaire (DMQ)		X				
Comprehensive Relative Autonomy Index for Drinking (CRAI Drinking)		X				
Alcohol Sensitivity Questionnaire (ASQ)		X				
Impaired Control Scale (ICS)		X				
Dietary supplement or placebo			X	X		
Administer alcohol priming drink			X	X		
Paced alcohol or control drinking			X	X		
Weight and height			X			
Pregnancy test			X	X		
Alcohol-specific satiety questionnaire			X	X		
Drug Effects Questionnaire (DEQ)			X	X	X	
Visual Analogue Scale (VAS)			X	X		
Biphasic Alcohol Effects Scale (BAES)			X	X		
Subjective Effects of Alcohol Scale (SEAS)			X	X		
Alcohol Urge Questionnaire (AUQ)			X	X		
Alcohol Purchase Task (APT)			X	X		
Dot Probe task			X	X		
Breath Alcohol Concentration (BrAC)			X	X	X	
Transdermal Alcohol Concentration (TAC), measured via Skyn			X	X	X	
Ecological Momentary Assessment (EMA)					X	
DEXA scan					X	
Venipuncture blood sample x2			X	X		
Fingerprick blood sample x3			X	X		
Timeline followback (TLFB)						X
Brief young adult alcohol consequences questionnaire						X
Importance of consequences of drinking short-form						X
Return Skyn monitor						X

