Increasing evidence also suggests that chronic alcohol consumption promotes neuroinflammation. Increases in systemic inflammation due to alcohol consumption are proposed to contribute both to alcohol-related diseases (including liver disease and cancers) and negative affective states in AUD (e.g., pain, stress). Examination of postmortem human brain tissue demonstrates increased proinflammatory signaling molecules in AUD – one such marker being high-mobility group box 1 (HMGB1) [46, 47]. Evidence from both human and animal brain tissue shows that HMGB1 is a key marker of alcohol-induced immune activation [46-51].

Summary

The goal of the proposed study is to collect pilot data on factors which may predict risk for alcohol use disorder through an inter-lab collaboration using data from 2 alcohol drinking laboratory visits and a 7-day remote assessment period. Correlations between Skyn TAC and BrAC will be assessed in an internally valid, controlled laboratory setting and in an ecologically valid natural setting within the same individuals, and to examine correspondence between TAC and BrAC in predicting alcohol consumption and alcohol-related harms among 42 moderate-heavy drinking adults. During laboratory sessions, additional aims related to individual differences in alcohol risk phenotypes will be assessed. Satiety to the effects of alcohol will be assessed using a novel self-report measure of alcohol-specific satiety and a laboratory model of paced drinking, and the effect of a GLP-1 stimulating dietary supplement on alcohol-specific satiety. In addition, individual differences on an inflammatory biomarker, HGMB1 on drinking outcomes will be assessed.

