naturalistic drinking contexts to assess the strength of the association between a novel TAC sensor (BACtrack Skyn) and breath alcohol (BrAC) measurements. In addition, we will also use a small non-intrusive light-based blood flow measurement device (placed on the participant's finger) and validate these measurements against the other metrics. These aims will be accomplished using data from two half-day visits to our lab at UNC campus, 1-2 days apart, followed by a 7-day remote assessment study and a final brief discharge visit (Figure 1). Lab visits involve a novel self-report questionnaire to assess alcohol-specific satiety during a paced alcohol challenge paradigm. In addition, on each of the two sessions in counterbalanced order, participants receive either a dietary supplement intended to stimulate postprandial GLP-1, or a calorically matched placebo to assess the effect of GLP-1 stimulation on alcohol-specific satiety. Two blood samples will be collected at each session to confirm plasma levels of glucagon-like peptide 1 (GLP-1). Blood fingerprick samples will be used to measure high-mobility group box 1 (HMGB1) inflammatory marker at three timepoints after alcohol administration. Additional measures of reward and incentive motivation for alcohol will be included to test the hypothesis that satiety is associated with reduced incentive motivation for alcohol reward. At the end of the second lab visit participants will be oriented to the 7-day remote assessment study. During the 7-day remote visit participants will be asked to wear the Skyn sensor continuously across 24-hours/day, except when bathing/showering or charging the device, and to initiate EMAs if they start an alcohol drinking bout. During drinking bouts, and for up to one hour following drinking bouts, participants will be prompted to record their BrAC every 20 minutes and to self-report the number of drinks consumed since the prior survey and subjective intoxication. Each morning, participants will complete daily diaries reporting alcohol-related harms experienced on the prior day. Following the 7-day remote visit, participants will complete a final discharge visit to return study devices, complete a timeline follow-back, and undergo a dual x-ray absorptiometry (DEXA) scan to assess fat-free mass, which will be included as a covariate in subsequent analyses to account for alcohol-elimination rate [56]..

[figure not shown]

Figure 1. Diagram of lab session procedures

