To analyze study aim 3, multi-level regression models will be used to assess within-person changes on repeated measures along with between-person individual differences. A linear growth curve model will be used to test the hypothesis that alcohol-specific satiety increases with time and additional drinks. Timepoint (1-6) and drug (alcohol or placebo) will be included in the model as within subject factors. Compared to placebo, alcohol is predicted to be associated with higher rates of change (slope) in satiety. Next, AUDIT will be included as a continuous predictor of slope in the model to test the hypothesis that participants with fewer alcohol dependence symptoms (lower AUDIT scores) report reduced satiety. Finally, subjective craving scores (Alcohol Urge Questionnaire; AUQ) from each timepoint will be included in the model. The effect of satiety over time is expected to remain significant after controlling for craving. Alcohol-specific satiety is expected to be negatively associated with measures of reward and incentive motivation for alcohol (BAES, APT, Dot Probe). Outcomes from each of these measures will be included in separate multi-level models with satiety scores as the primary dependent measure and timepoint (1-6) and drug (alcohol, placebo) as within-subject factors to determine the effect of additional dependent measures on within-person change in alcohol specific-satiety over time (slope).

To analyze aim 4, a repeated measures analysis of variance (ANOVA) will be used to assess the effect of a dietary supplement on alcohol-specific satiety in a 2(alcohol, placebo) x 2(timepoints) design. It is

predicted that compared to placebo, a GLP-1 stimulating dietary supplement will increase alcohol-specific satiety.

To analyze aim 5, linear regression will be used to assess the association between HMGB1 levels as a function of BrAC during the laboratory alcohol sessions. Data processing and analyses will be completed in R and SPSS.

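### The Aim 4 ANOVA names the drink factor instead of the supplement, leaves its two timepoints undefined, and no satiety model holds both supplement and drink

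*Combined protocol and SAP*

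**What the plan says.** Section 8.1 gives Aim 4 a repeated-measures ANOVA to "assess the effect of a dietary supplement on alcohol-specific satiety in a 2(alcohol, placebo) x 2(timepoints) design". The next sentence states the hypothesis: it is "predicted that compared to placebo, a GLP-1 stimulating dietary supplement will increase alcohol-specific satiety". The plan does not say which two timepoints are meant, or which term of the ANOVA carries the hypothesis.

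The Aim 3 paragraph of the same section uses the same pair of labels for the drink. For the growth model, "Timepoint (1-6) and drug (alcohol or placebo) will be included in the model as within subject factors". The further Aim 3 models use "timepoint (1-6) and drug (alcohol, placebo) as within-subject factors". The Aim 3 hypothesis concerns a slope: "Compared to placebo, alcohol is predicted to be associated with higher rates of change (slope) in satiety". No Aim 3 model contains the supplement.

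Two things are manipulated over the same two laboratory visits:

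- **Supplement.** Section 4.1: "on each of the two sessions in counterbalanced order, participants receive either a dietary supplement" or a matched placebo.
- **Paced drink.** The Schedule of Activities (Section 1.2) has a row "Paced alcohol or control drinking", marked at both visits. Section 4.3 describes five mini-drinks that contain alcohol or placebo, and refers to a control session.

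An alcohol priming drink is given at both visits (Section 1.2). Section 4.3 places satiety assessments after the priming drink and again after each mini-drink, and has outcome measures taken at baseline. Section 3 lists plasma GLP-1 as an Aim 4 outcome, but Section 8.1 gives no test of it.

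**The concern.** Three things decide what Aim 4 estimates: which factor is in the model, which two satiety scores are used, and how supplement and drink conditions are paired across a person's two sessions. The first is written wrongly, the second is not stated, and the third is not in the readable text (Figure 1, the diagram of lab session procedures, is not shown).

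Read literally, the ANOVA compares drink conditions and does not test its own hypothesis. Read as a slip, it has a supplement term but no drink term. Either way no satiety model accounts for both manipulations, although each person fills only two of the four supplement-by-drink combinations. If a chosen timepoint falls after paced drinking starts, part of a drink effect could be reported as a supplement effect. Aim 3 itself predicts a drink effect on satiety, so this is not a remote possibility on the plan's own reasoning.

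**Working it through.** **1. Which measurements are exposed.** The order within a session (Section 4.3) is: baseline, supplement, blood sample at 45 minutes, priming drink, satiety, then five mini-drinks with satiety after each. Baseline, 45-minute GLP-1 and post-priming satiety all come before that session's paced drinks. Only later satiety scores can carry the drink condition.

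**2. What a supplement-only contrast estimates on later scores.** Let S be the supplement effect, A the drink effect, and q the share of participants whose supplement session is their alcohol session. The person-level difference, supplement session minus placebo-supplement session, has mean S + A for share q and S - A for share 1 - q. The average is S + (2q-1)A. The multiplier of A is -1, -0.5, 0, 0.5 and 1 for q = 0, 0.25, 0.5, 0.75 and 1.

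**3. Can both effects be estimated?** Take 42 people, two sessions each, with person effects in the model. The supplement and drink columns add rank 1 if pairing is fixed (not separable) and rank 2 if pairing is split evenly (both estimable; rank 3 with visit).

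**4. Size.** The documents give no satiety effect sizes, so these are assumptions: SD of the person-level contrast 1, two-sided alpha 0.05, N = 42 (the completer target in Section 4.2 and the figure in Section 8.2). Section 8.2's 86% power cannot be reproduced uniquely, because groups, number of measurements and correlation are not given. Nothing here rests on it. In a 2 x 2 within-person ANOVA each one-degree-of-freedom F is the square of the one-sample t on the person-level contrast, so the contrast results apply to the planned analysis.

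*Balanced pairing, 21/21, drink omitted.* There is no bias, but the drink effect inflates the residual. The true SE is 1/sqrt(42) = 0.154. For A = 0.5 the estimated SE is about sqrt((1 + 0.25 x 42/41)/42) = 0.173.

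| Drink effect A (SD) | Type I error | Power for S = 0.5 |
|---|---|---|
| 0.5 | 2.7% | 83% |
| 0.8 | 1.3% | 74% |
| 1.0 | 0.6% | 64% |
| any, drink in the model | about 5% | about 89% |

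*Uneven pairing, 28/14, drink omitted, S = 0.* 2q - 1 = (28 - 14)/42 = 1/3. For A = 0.3, 0.5, 0.8 the bias is 0.10, 0.17, 0.27 SD, and the false-positive rate is about 8%, 13%, 22%. If drink were allocated independently of supplement, a split this uneven or worse has probability of about 4% (binomial, n = 42, p = 0.5, both tails).

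*Fixed pairing, S = 0.* The whole of A appears as a supplement effect. For A = 0.3, 0.5, 0.8 the test rejects 48%, 89%, 99.9% of the time (noncentral t, 41 df).

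**5. Aim 3.** The hypothesis is drink x timepoint. A supplement effect that is constant over timepoints 1-6 moves only the drink main effect: simulated slope bias was 0, with rejection of 4.7% (fixed) and 5.0% (28/14). A supplement effect on slope of 0.5 SD gives a drink-slope bias of 0.50 under fixed pairing and 0.17 under 28/14. Adding supplement x timepoint restores about 5% rejection under 28/14.

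**The case against.** The wording error nearly corrects itself: the following sentence states the contrast, the section is a summary, and the study is a pilot. That is fair, and taken alone the label is a one-word change. It does not supply the timepoints, the test term or the second factor.

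A reader might infer that supplement and drink are confounded and take 89% or 99.9% as the error rate of Aim 4. The documents do not support this. Those figures need fixed pairing for everyone, an Aim 4 timepoint after paced drinking starts, and an assumed drink effect. None of the three is in the readable text. Supplement order is counterbalanced, so if every participant had the drinks in the same order, an even split of supplement order would make the pairing exactly balanced. Independent allocation would keep it close to balanced. Deliberate yoking cannot be excluded, but it is only one scenario.

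A reader might also see a contradiction between the Background, which speaks of "using data from 2 alcohol drinking laboratory visits and a 7-day remote assessment period", and the control session in Section 4.3. There is none, because both visits include an alcohol priming drink.

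Finally, a reader might infer that the estimate will be halved, by averaging over a pre-supplement baseline. That presumes the supplement main effect will be read, which the plan does not say. The ANOVA also yields the interaction. What stands is that the test term should be named.

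**Conclusion.** The point holds in limited form and should be fixed. Certain from the text: the Aim 4 factor is mislabelled, so the model as written has no supplement term; its two timepoints are not named; no Aim 3 or Aim 4 satiety model holds both manipulations; and a listed Aim 4 outcome, GLP-1, has no test.

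The consequence depends on the pairing and the timepoints. If both Aim 4 timepoints precede paced drinking, the relabelled ANOVA is sound. If a later score is used and pairing is balanced, the cost is power only, about 83% instead of 89% under the 0.5 SD assumptions. If a later score is used and pairing is fixed, supplement and drink effects on that score cannot be separated. The Aim 3 slope test is at risk only if the supplement effect changes over timepoints and pairing is fixed or uneven. Confidence is high for the wording and model gaps. Bias is possible but not shown.

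**What to change.** 1. Relabel the Aim 4 factor as supplement against placebo supplement. Name the two timepoints and the single term that tests the hypothesis. If one timepoint is before the supplement, choose in advance either supplement x timepoint or the post-supplement score adjusted for that session's baseline.
2. In every satiety model that uses scores after paced drinking starts, including Aim 3, include supplement, drink and visit, with their timepoint interactions where slope is tested. If both Aim 4 timepoints precede paced drinking, the relabelled ANOVA with a visit term is enough.
3. State how supplement and drink are paired. If the pairing was fixed, limit the Aim 4 satiety test to the post-priming score, and report the Aim 3 drink effect on slope as not separable from any supplement effect that changes over time. If sessions remain and the pairing is not already balanced, counterbalance drink independently of supplement.
4. Add a test of 45-minute GLP-1 by supplement, adjusted for that session's baseline.

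The cost is plan wording, a little more analysis and possibly a revised allocation list for sessions not yet run. No visits or participants are added. Sessions already run under fixed pairing cannot be rescued for paced-drinking satiety, and the documents do not say whether allocation has begun.

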1. SUMMARY

1.1 SYNOPSIS

Title:	Satiety and transdermal alcohol concentration (SatTAC)
Study Description:	The proposed study is an inter-lab collaboration to gather pilot data on responses to alcohol in a controlled laboratory setting compared to a naturalistic setting. Alcohol is administered in the lab and alcohol exposure is measured with a wearable wrist monitor (Skyn) and a breathalyzer (BACtrack S80). Naturalistic drinking and alcohol-related harms are assessed during a 7-day remote assessment period. Additional aims assessed during laboratory visits include changes in satiety to alcohol after dietary manipulation and the relationship between responses to alcohol and biomarkers: GLP-1 and HMGB1.
Objectives:	
Aim 1: Identify the correlations between transdermal alcohol concentration (TAC; Skyn) and breath alcohol concentration (BrAC; BACtrack S80) in controlled laboratory and natural settings and compare correlations across settings.
 
Aim 2: Compare TAC and BrAC as predictors of self-reported number of drinks consumed and the odds and frequency of alcohol-related harms in natural settings.
 
Aim 3: Model individual differences in alcohol-specific satiety using self-report and a paced-drinking alcohol administration laboratory model.
 
Aim 4: Assess the effect of a dietary supplement on plasma GLP-1 levels and subjective and alcohol satiety.
 
Aim 5: Assess the effect of acute alcohol exposure on a marker of peripheral inflammation (HMGB1)

Outcomes:	
Alcohol exposure: Transdermal alcohol concentration, breath alcohol concentration. Questionnaires: Self-reported satiety questionnaire and other alcohol subjective response questionnaires. Tasks: Behavioral economic demand for alcohol, attentional bias to alcohol-related cues. Remote self-reported assessment of alcohol-related harms. Biomarkers: Plasma change in GLP-1 and HMGB1.

Study Population:	Adults from the triangle area (Chapel Hill, Raleigh, Durham) who meet NIAAA criteria for at-risk drinking; >7/14 standard drinks per week for women/men, with at least one past-month heavy drinking episode defined as 4/5+ standard drinks for women/men.
Description of Sites/Facilities Enrolling:	University of North Carolina at Chapel Hill
Participants:	55
Study Duration:	1 year

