3. OBJECTIVE AND OUTCOME MEASURES

Aim 1: Identify the correlations between transdermal alcohol concentration (TAC) and breath alcohol concentration (BrAC) in controlled laboratory and natural settings and compare correlations across settings.

- Outcomes measures: BrAC using the BACtrack S80 and TAC readings using the BACtrack Skyn monitor and light-based finger monitor during laboratory alcohol drinking sessions and a remote assessment period.

Aim 2: Compare TAC and BrAC as predictors of self-reported number of drinks consumed and the odds and frequency of alcohol-related harms in natural settings.

- Outcome measures: BrAC and TAC readings, self-reported number of drinks and alcohol related harms measured using a mobile app questionnaire (LifeData app).

Aim 3: Model individual differences in alcohol-specific satiety using self-report and a paced-drinking alcohol administration laboratory model.

- Outcome measures: Alcohol specific satiety questionnaire, BrAC readings.
- Secondary measures: Self-report alcohol subjective effects (stimulation, sedation, craving), behavioral economic demand for alcohol, attentional bias for alcohol related cues.

Aim 4: Assess the effect of a dietary supplement on satiety to alcohol

- Outcome measures: Blood plasma GLP-1 levels samples during lab sessions via venipuncture before and after supplement administration, alcohol-specific satiety questionnaire

Aim 5: Assess the effect of alcohol exposure on HMBG-1 marker of inflammation

- Outcome measures: Blood plasma levels of HMBG-1 will sampled during lab sessions via fingerprick at timepoints before alcohol administration, 30 minutes after an initial priming drink, and after the final drink.

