4.3 STUDY VISIT PROCEDURES

Participants will arrive to the lab at 9 AM fasted overnight prior to the alcohol administration study visits. Identity will be confirmed by verification of photo ID and pregnancy will be confirmed with a urine pregnancy screen. Abstinence from alcohol will be confirmed with a breathalyzer. Mode of transportation to the session will be confirmed. Participants will be encouraged to arrange for a ride or take public transportation to sessions to minimize the risk of driving while intoxicated. In the case that a participant drives themselves to the session, the participant will be required to sign an acknowledgment that their keys will be held by the research assistant during the session and returned after the subject's BAC reaches zero. Blood will be sampled with venipuncture to analyze baseline plasma GLP-1. Fingerprick blood sample will be used to measure HMGB1. Baseline measurements of study outcomes will be taken at this time. Participant will complete additional baseline measures at home including: demographics form, the Alcohol Use Disorder Identification Test (AUDIT) [57], Obsessive Compulsive Drinking Scale (OCDS) [58], Reward-based Eating Drive Scale (RBEDS) [59], Body Perception Questionnaire (BPQ) [60], Drinking Motives Questionnaire (DMQ) [61], Comprehensive Relative Autonomy Index for Drinking (CRAI Drinking) [62], Alcohol Sensitivity Questionnaire (ASQ) [63], and the Impaired Control Scale (ICS) [64], and the Inventory of Drinking Situations (IDS) [65] using REDCap to explore potential moderators in secondary analyses. Assessments will occur in a study room furnished to feel like a comfortable living room with a TV. Participants may watch TV or engage in relaxing recreational activities (e.g. reading, personal computer) during recovery from alcohol. Participants will be fitted with a Skyn TAC wrist monitor and finger-tip sensor to monitor alcohol exposure and be trained on using the BACtrack S80 for BrAC measures. Participants will download the Skyn app to sync the Skyn data during the session, and then will be instructed to refrain from using their phones for non-study related purposes.

Dietary manipulation

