Participants will receive a beverage containing either a dietary supplement (10g Fibersol®-2 mixed with water and aspartame sweetener for taste + 725mg decaffeinated green tea extract capsule) or a calorically matched placebo supplement (Aspartame sweetener mixed with water + aspartame capsule) counterbalanced at two separate visits. Forty-five minutes after the dietary supplement, the second blood sample is taken. Next, a priming drink (calculated to achieve 30mg% BAC) is administered to stimulate craving for alcohol [66, 67]. Drinks will consist of 40 proof vodka and a sugar-free cranberry juice mixer at a 1:5 ratio. Doses are calculated to achieve target BACs based on sex and body weight using formulas established in prior research [68]. Fifteen minutes after the priming drink, a novel alcohol-specific satiety questionnaire will be administered followed by alcohol incentive motivation tasks (alcohol purchase task; APT [69], dot probe attentional bias to alcohol-related stimuli), additional validated alcohol subjective response questionnaires (Drug Effects Questionnaire; DEQ[70], Biphasic Alcohol Effects Scale; BAES [71], Alcohol Urge Questionnaire; AUQ [72], Subjective Effects of Alcohol Scale; SEAS [73]), *hunger, fullness, and satiety* visual analogue scale (VAS) items, a BACtrack S80 BrAC measure, and a fingerprick blood sample.

Alcohol-specific satiety paced drinking procedure

Then over a 2-hour period, 5 additional mini-drinks (calculated to achieve an estimated BAC increase of 10mg% each or placebo) are administered with 15 min absorption time between each drink to reach an estimated maximum BAC of 60-70mg%, reflecting a moderate level of alcohol exposure (80mg% is the conventional cutoff for “binge” exposure). Participants have 3 minutes to finish each drink (Average volume of a drink, alcohol+mixer at a 1:5 ratio is 8/5oz for a man/woman). This paradigm is designed to approximate a natural drinking pace, while controlling for the BAC during subjective satiety assessment. The control session will control for expectations of increased satiety with subsequent drinks. Control drinks contain cranberry juice with an alcohol mask (rim sprayed with vodka) matched in total volume to the alcohol drinks. Participants will be told that all drinks contain alcohol. Subjective response questionnaires are repeated 15 minutes after each drink. BACtrack S80 BrAC measures are repeated every 15 minutes.

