After the paced drinking procedure, a final fingerprick blood sample will be taken and participants will remain in the lab until their BAC reaches 0mg% at which point they will be either dismissed. At the end of the second lab session, participants will receive instructions on using the Skyn and BACtrack S80 devices, using the Skyn app for syncing Skyn data and the LifeData app for completing drinking bout EMA surveys and morning surveys about past day alcohol use and consequences.

Remote assessment

During the 7-day naturalistic study, participants will be asked to wear the Skyn for 24 hours/day for 7-days (except when bathing or swimming). On days when participants choose to drink they will initiate drinking bout surveys via smartphone by indicating they have started drinking, after which they will be prompted to provide a BrAC reading once every 20-minutes throughout the drinking bout and for up to 1-hour after the drinking bout ends. Every 60-minutes participants will also self-report alcohol amount and subjective intoxication during the drinking bout. Importantly, participants will be informed that they are not expected to change their drinking behaviors during the study and compensation is not contingent on self-reports or breathalyzer readings during drinking bouts. Participants will complete daily morning surveys about past day alcohol use and consequences and evening surveys about daily pain and stress.

After the 7-day protocol, participants will return their devices to the PI's lab and report past 7-day drinking behaviors (timeline follow-back; TLFB) and drinking consequences (Brief Young Adult Alcohol Consequences Questionnaire, Importance of Consequences of Drinking short-form) and undergo a DEXA scan. Participants will be compensated upon device return with up to \$240 (\$20 for baseline surveys, \$50 for lab visit one, \$50 for lab visit two, \$70 for all 7-day EMA study procedures, \$10 for device return, \$10 for follow-up questionnaires, \$10 for DEXA scan, and \$10 study completion bonus).

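### Aim 5 regresses repeated HMGB1 levels on BrAC with no participant term, time term or analysis unit, so drift over a session can be credited to alcohol

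*Combined protocol and SAP*

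**What the plan says.** Section 8.1 gives Aim 5 one analysis sentence: "linear regression will be used to assess the association between HMGB1 levels as a function of BrAC during the laboratory alcohol sessions". The synopsis lists the outcome as "Plasma change in GLP-1 and HMGB1", and states the aim as the effect of acute alcohol exposure.

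The Schedule of Activities marks three fingerpricks at each of the two study visits. Section 4.3 places them at baseline ("Fingerprick blood sample will be used to measure HMGB1"), in the assessment block after the priming drink ("a BACtrack S80 BrAC measure, and a fingerprick blood sample"), and after paced drinking, when "a final fingerprick blood sample will be taken". Section 3 agrees: samples are taken "via fingerprick at timepoints before alcohol administration, 30 minutes after an initial priming drink, and after the final drink". Section 4.1 words it differently: "high-mobility group box 1 (HMGB1) inflammatory marker at three timepoints after alcohol administration".

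The main analyses for the other aims deal with repeated data. Aims 1 to 3 use multi-level models and Aim 4 a repeated-measures ANOVA. For Aim 3, "Timepoint (1-6) and drug (alcohol or placebo) will be included in the model as within subject factors". Nothing of this kind is carried over to Aim 5.

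**The concern.** Forty-two completers with six samples each give 42 × 6 = 252 HMGB1 values from 42 people. A linear regression of levels on BrAC with no participant term treats these as independent, so its standard error is wrong.

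The missing time term matters more. Alcohol is given on a fixed schedule, so within the alcohol session BrAC and sample time rise together. Participants arrive fasted, drink repeatedly and are pricked three times. Any change in HMGB1 from these causes, or from the time of day, would load onto the BrAC slope and be reported as an effect of alcohol. The control drinking session could separate the two, but the plan does not say that Aim 5 uses it. It also does not say which of the 15-minute BrAC readings goes with each HMGB1 sample.

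**Working it through.** **Plan's own figure.** There is none for this regression. The N = 42 and 86% power in section 8.2 refer to a within-between interaction on repeated measures.

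**Inputs from the documents.** 42 completers; three samples at each of two visits; peak target 60-70 mg% (65 used); priming target 30 mg%.

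**Assumed inputs.**
- Intraclass correlation (ICC) 0.3, 0.5 and 0.7.
- BrAC 0/30/65 mg% with alcohol drinks and 0/30/15 with control drinks, with relative SD 0.15.
- Sample clock 0/75/210 minutes: 45 from supplement to priming drink, plus 30, then 120 of paced drinking, plus 15.
- Drift linear on that clock. Drift is in HMGB1 SD over the session, and effects are in SD per 65 mg%.

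**Step 1: share of drift that enters the pooled slope.** With x = BrAC and t = minutes, the share per 65 mg% is (65/210) × Sxt/Sxx.
- Alcohol session: Sxt = 6,875, Sxx = 2,116.7, Stt = 22,650. Correlation = 6,875/√(22,650 × 2,116.7) = 0.99. Share = 0.3095 × 3.248 = 1.01.
- Both visits: Sxt = 8,000, Sxx = 2,983.3, Stt = 45,300. Correlation = 8,000/√(45,300 × 2,983.3) = 0.69. Share = 0.3095 × 2.682 = 0.83.

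With the BrAC scatter added, the shares are 0.95 and 0.79. If control BrAC ends at 0 or 25 mg% instead of 15, the both-visit share is 0.55 or 0.94.

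**Step 2: type I error of pooled regression, no alcohol effect (simulated).**

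| Drift | Type I error, ICC 0.3-0.7 |
|---|---|
| none, equal slopes | 0-2% |
| 0.3 SD | 15-23% |
| 0.5 SD | 62-68% |

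Repeat runs differ by a few points. Varying the control end-point from 0 to 25 mg% widens the both-visit range to 6-32% at 0.3 SD and 27-85% at 0.5 SD. A model with participant effects and categorical time stays at about 4-6%.

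**Step 3: the standard error without drift.** With equal BrAC slopes across people, the pooled standard error is 1.2/1.35/1.6 times the true value at ICC 0.3/0.5/0.7. With a slope SD of 1.0 the ratio is 0.84/0.95/0.98 and type I error 10/7/5%. With a slope SD of 1.5 the ratio is 0.75-0.81 and type I error 11-15%. The error can therefore go either way.

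**Step 4: the change-score reading.** Drift common to everyone falls into the intercept, and type I error is about 5%. Power for a 0.5 SD effect:

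| Analysis | ICC 0.3 / 0.5 / 0.7 |
|---|---|
| one row per person, alcohol session, on peak BrAC | about 7-9% |
| one row per session, change on BrAC change | about 34 / 44 / 65% |
| within-person model, all samples, categorical time | about 58 / 70 / 90% |

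The first row depends on the BrAC scatter. At ICC 0.5 it rises from 8% to 15% and 24% as the relative SD goes from 0.15 to 0.3 and 0.4.

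**The case against.** The plan does not say that rows are pooled. Section 8.1 summarises strategy, and the background summary describes the HMGB1 aim in terms of individual differences, which suggests a person-level analysis. With the synopsis outcome of change and one row per session, ordinary linear regression would handle common drift with moderate power. This stands in part. The text allows several readings, and the large false-positive rates belong to only one. But that one fits the stated outcome of levels best, and no section rules it out.

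The harm figures rest wholly on assumed drift, ICC and slope variation. That also stands. A reader might infer that ignoring the clustering must inflate type I error. The check does not support that: with no drift and similar slopes, pooling is conservative. Inflation needs drift or widely differing slopes.

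A reader might also infer that a change-score analysis could not detect a plausible effect. That fits only the one-row-per-person form, and even there it depends on the assumed BrAC scatter.

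Finally, section 3's 30 minutes for the second sample may seem to conflict with section 4.3, where the block starts 15 minutes after the priming drink. It does not. The block includes the purchase task (up to 5 minutes), the dot probe (5 minutes) and questionnaires, and the fingerprick is listed last.

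**Conclusion.** The concern holds as a gap in method. The Aim 5 sentence names a model that, applied to levels, ignores that samples come in sets of six per person and that BrAC tracks sample time. Under the assumed values, pooled type I error runs from about 0-2% with no drift to 62-68% with 0.5 SD of drift. The change-score alternative is protected from common drift but is less efficient. These readings differ enough that the choice should be fixed before the data are seen.

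Confidence is high that the specification is missing and low on the size of the bias, because the documents give no HMGB1 variance, drift or time course. They do not support a claim that the Aim 5 result will be badly biased, only that the stated method gives no protection if drift exists. As this is the fifth aim of a pilot, it is a low-end should-fix.

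**What to change.** Replace the Aim 5 sentence with a linear mixed model on all HMGB1 samples from both visits:
- random intercepts for participant and for session;
- fixed effects for categorical sample time, supplement, visit number and person-mean BrAC;
- participant-clustered small-sample standard errors, or a random BrAC slope. Random intercepts alone gave 9-17% type I error at slope SD 1.0-1.5;
- a test of the within-person BrAC slope.

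State that each HMGB1 sample is paired with the BrAC reading closest in time. State also that the time-adjusted slope mainly reflects the paced mini-drinks: the priming drink is given at both visits, so categorical time absorbs its average effect. This is narrower than acute alcohol exposure as a whole. Reconcile levels in section 8.1 with change in the synopsis, and section 4.1's placing of all three samples after alcohol with the pre-alcohol sample in sections 3 and 4.3.

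The cost is wording and slightly more analysis work, with no new samples. If there is truly no drift, nominal power for a 0.5 SD effect is lower than with pooling: about 58/70/90% against 83/85/91% at ICC 0.3/0.5/0.7, a loss of 25, 15 and 1 points. Pooling's extra power comes partly from change over sample time, so it can be relied on only if drift is known to be absent.
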